### A. Specific Aims

The long term objective of this study is to establish objective measurements of musculoskeletal changes that occur in response to osteopathic manipulative treatment (OMT). Many patients who suffer from low back pain (LBP) receive OMT to the lumbar, pelvic, sacral, and lower extremity body regions that helps resolve or manage their pain. The indication for OMT in a patient suffering from LBP is the presence of somatic dysfunction found during the physical examination. Somatic dysfunction is diagnosed when one or more of the following physical findings are present: tenderness, asymmetry, restricted range of motion, and tissue texture abnormalities. OMT is performed to specifically target these physical findings, after which the patient is reassessed for a reduction or resolution of the findings. In the clinical setting the assessment and reassessment of somatic dysfunction is performed using palpatory examination. Because palpatory findings commonly demonstrate poor interexaminer reliability, the proposed study will use ultrasound to establish pre- and postOMT musculoskeletal measurements of the relative asymmetry between the participants' pelvic and sacral bony landmarks. The investigators will use a control group to compare the changes in the pre and post OMT measurements to participants who have not received OMT. If ultrasonography is able to detect a significant change in the relative asymmetry between the pelvis and sacrum, then ultrasound may be useful for assessing and quantifying outcomes for OMT in a variety of body regions such as spine, shoulders, and knees. To determine if ultrasound is a reliable objective measure to assess OMT outcomes in LBP patients the following specific aims are proposed:

- Determine if ultrasound measurements of sacral landmarks are stable over 30 minutes in untreated participants.
- Determine the extent to which OMT affects the relative asymmetry between the pelvic and sacral landmarks as measured by ultrasonography.
- Determine if ultrasound measurements of sacral base asymmetry agree with palpatory assessment.

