### **C. Purpose Statement and Hypotheses**

The objective of the proposed study is to quantify the change in sacral base asymmetry as measured by ultrasonography before and after OMT. The proposed study will utilize a control group to determine the stability of the sacral measurements and compare those findings to a treatment group that will receive OMT to

specifically address sacral somatic dysfunction as identified clinically. The proposed study will also compare the clinical palpatory assessment of sacral base asymmetry to the ultrasound measurements. Since the primary aim of this study is to assess the effect of OMT on sacral base asymmetry, the investigators will recruit participants with a recent history of LBP to ensure a high likelihood that the participants will have sacral

[figure not shown]

Figure 1. (A) Posterior view of the pelvis. The sacral base is the posterior superior surface of the sacrum divided into the right sacral base and the left sacral base. Posterior superior iliac spines (PSIS) are tubercles that project posteriorly from the posteromedial portion of the iliac bones on either side. (B) Superior view of the posterior pelvis. Sacral bases are traditionally palpated to assess for asymmetry by determining the relative anterior or posterior positioning of each sacral base and the relative depth of each sacral sulcus (deep or shallow).

somatic dysfunction which would include sacral base asymmetry. This assumption is based on several studies that have found that people with LBP have a significantly greater incidence and severity of somatic dysfunction in the lumbar, pelvic and sacral regions than people without LBP.

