## Data analysis

Power calculations performed on preliminary SSDD data suggested that recruiting 38 participants would allow us to detect mean difference of  $\pm 0.5$  cm in the two treatment groups at pre-post treatment analysis at 0.05 significance level with 80% power. We plan to recruit 40 participants total (20 in each group). While the students, who collected the preliminary data, were not expert ultrasonographers, the quantity of data allows for an estimation of the likely range of measurements that will be seen in the proposed study. Descriptive statistics such as means, ranges, and standard deviations (SD) for continuous variables and frequency and percent will be used to summarize the categorical data. Two sample *t*-tests will be used to compare mean age and BMI across groups.

Correlations between BMI and US measurements will be calculated for each landmark (SPSIS, SSB, SSD). Absolute asymmetry between left and right landmark measurements will be calculated as follows:

$$\text{absolute asymmetry} = |\text{landmark}_{\text{left}} - \text{landmark}_{\text{right}}|$$

To determine if absolute asymmetry increased, decreased, or stayed the same after intervention, direction of change in asymmetry will be calculated as follows:

$$\begin{aligned}\text{direction of change in asymmetry} &= |2^{\text{nd}} \text{ US landmark}_{\text{left}} - 2^{\text{nd}} \text{ US landmark}_{\text{right}}| >, <, \text{ or} \\ &= |1^{\text{st}} \text{ US landmark}_{\text{left}} - 1^{\text{st}} \text{ US landmark}_{\text{right}}|\end{aligned}$$

To account for total change in measurements at both left and right landmarks between the first and second US measurements, total change in asymmetry between first and second US assessments will be calculated as follows:

$$\text{total change in asymmetry} = |(1^{\text{st}} \text{ US landmark}_{\text{left}} - 1^{\text{st}} \text{ US landmark}_{\text{right}}) - (2^{\text{nd}} \text{ US landmark}_{\text{left}} - 2^{\text{nd}} \text{ US landmark}_{\text{right}})|$$

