The Fisher exact test is to be used to test associations between group and direction of change in asymmetry at each landmark. Multiple linear regression models will be built to compare mean absolute asymmetry for each landmark measured during the first US assessment between groups while controlling for demographic characteristics, date of last pain, and frequency of pain. Similar multiple linear regression models will be built to compare mean total change in asymmetry from first to second US assessment between groups for each landmark between groups.

Mean absolute asymmetry at the first and second US assessments and mean total change in asymmetry for seated control and OMT groups will be compared using a 2-sample t test. To compare qualitative palpitory assessment of SBP and SSD with quantitative US measurements, US measurement of landmark position will be first converted to a qualitative assessment as follows:

- right anterior SBP or deep SSD = right US measurement > left US measurement
- right posterior SBP or shallow SSD = right US measurement < left landmark measurement
- equal SBP or SSD = right US measurement = left US measurement

To compare agreement between qualitative palpitory and US assessments of SBP and SSD,  $\kappa$  and associated 95% CIs will be calculated. Values less than or equal to 0 indicated no agreement; 0.01 to 0.20, none to slight; 0.21 to 0.40, fair; 0.41 to 0.60, moderate; 0.61 to 0.80, substantial; and 0.81 to 1.00, almost perfect agreement.

To determine if US localization of landmarks at the sacral base was reliable, intraclass correlation coefficients (ICC) and associated 95% CIs will be calculated for US measurements from the first to second US assessment for each landmark. For ICC, 0.7 to 0.8 was considered good; 0.8 to 0.9, very good; and 0.9 to 1.0, excellent.  $P \leq 0.05$  was considered significant. Data analysis will be performed using SAS statistical software version 9.4 (SAS Institute, Inc.).

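### The reliability ICCs cover one-side depths and name no group, while the left-right difference on which OMT is judged has no planned reliability statistic

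*Combined protocol and SAP*

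**What the plan says.** The Data analysis section introduces the reliability analysis with "To determine if US localization of landmarks at the sacral base was reliable" and then plans that "intraclass correlation coefficients (ICC) and associated 95% CIs will be calculated for US measurements from the first to second US assessment for each landmark". The same section lists the landmarks as SPSIS, SSB and SSD and uses left and right only as subscripts. The natural reading is therefore that each ICC concerns a depth on one side. The plan does not say whether the sides are analysed separately or together, which form of ICC is meant, or which participants are included. The labels are set as "For ICC, 0.7 to 0.8 was considered good; 0.8 to 0.9, very good; and 0.9 to 1.0, excellent".

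Elsewhere, stability belongs to the untreated arm. The first Specific Aim reads "Determine if ultrasound measurements of sacral landmarks are stable over 30 minutes in untreated participants", and section C says "The proposed study will utilize a control group to determine the stability of the sacral measurements". Potential Limitations gives the control group the same role. None of these places names a statistic.

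The three measures used to judge OMT (absolute asymmetry, direction of change, total change in asymmetry) are all built on left minus right. They are planned as comparisons between arms; for example, "mean total change in asymmetry for seated control and OMT groups will be compared using a 2-sample t test".

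**The concern.** The sentence that introduces the Specific Aims asks something wider than localization: whether ultrasound is reliable for assessing the result of OMT. The quantity that answers this is the left-right difference, not the depth on one side. On subtraction, the between-person spread shared by the two sides cancels, while the measurement errors of both sides remain unless they are correlated. The difference can then be clearly less reliable than either depth.

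At stake is the measurement conclusion. A report that follows the plan could call the depths *very good* while the reliability of the variable on which OMT is judged has not been estimated. The unnamed group is a smaller, related gap. If treated participants entered the ICC, a real OMT effect would count as disagreement between the two assessments.

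**Working it through.** The plan states no ICC value and no precision target, so there is no figure of its own to reproduce on this point. Table 1 is consistent in its means: right SSD 1.98 minus left SSD 1.88 gives the tabulated SSDD of 0.10 cm.

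**Inputs.** From Table 1 (Preliminary Data): SD of left SSD 0.59, of right SSD 0.63, of SSDD 0.57 cm. Assumptions that are not in the documents: the same ICC, R, on both sides, and a correlation c between the left and right errors.

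**Step 1, implied left-right correlation of SSD.** The two variances sum to 0.59² + 0.63² = 0.745; 0.57² = 0.3249; 0.59 × 0.63 = 0.3717. So ρ = (0.745 − 0.3249) / (2 × 0.3717) = 0.565.

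**Step 2, reliability of the difference.** Error variance of SSDD: E = (1 − R)(0.745 − 2c × 0.3717). Reliability = 1 − E / 0.3249.

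- c = 0: E = 0.2235, 0.149, 0.0745 for R = 0.70, 0.80, 0.90. Reliability is 0.31, 0.54, 0.77.
- On the measured scale at c = 0, the within-person SD is √E = 0.47, 0.39, 0.27 cm. The 95% limits of agreement are ±1.96√(2E) = ±1.31, ±1.07, ±0.76 cm.
- c = 0.5: the bracket is 0.3733. Reliability is 0.66, 0.77, 0.89.
- c = 0.565: the bracket equals 0.3249, so the difference is exactly as reliable as one side.
- At c = 0, a difference ICC of 0.70 (the lower edge of *good*) needs R = 1 − 0.30 × 0.3249 / 0.745 = 0.87.

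**Step 3, other left-right correlations.** Keep the one-side SDs and c = 0, and replace 0.3249 by 0.745 − 2ρ × 0.3717. This is 0.522 at ρ = 0.3 and 0.2246 at ρ = 0.7.

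| Assumption | R = 0.70 | R = 0.80 | R = 0.90 |
|---|---|---|---|
| ρ = 0.565, c = 0 | 0.31 | 0.54 | 0.77 |
| ρ = 0.565, c = 0.5 | 0.66 | 0.77 | 0.89 |
| ρ = 0.3, c = 0 | 0.57 | 0.71 | 0.86 |
| ρ = 0.7, c = 0 | about 0.00 | 0.34 | 0.67 |

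The same cannot be done for SSB or SPSIS, because Table 1 gives no SD for their left-right differences.

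**Step 4, effect of pooling the arms.** This was simulated with 400,000 participants, half treated, ρ = 0.565, independent errors, a one-way ICC, and OMT either halving or abolishing asymmetry with the change split between sides. An SSD ICC of 0.90 becomes 0.89 or 0.85, and 0.80 becomes 0.79 or 0.76. An SSDD ICC of 0.77 would fall to 0.67 or 0.47. Pooling matters little for the planned ICCs, and it lowers them. It matters more for an ICC of the difference.

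**The case against.** The strongest reply is that the information is already there. The plan yields control-arm total change, absolute asymmetry at both assessments and direction counts, as well as means, ranges and SDs of continuous variables. The mean and SD of total change give the mean squared change in the difference. The left and right means at each assessment give the signed shift. Together these recover the within-person SD and the limits of agreement. This stands in part. A reader might infer that nothing planned reflects error in the difference, and that would be wrong. But the plan does not say that the descriptives will be broken down by arm, side and assessment, and it presents these quantities as group comparisons or summaries. None is planned as a reliability statistic.

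Second, the ICC matches its stated purpose of localization, and no sentence says that its label will settle reliability for OMT outcomes. That is correct. The point is that the wider question in the Specific Aims has no planned reliability statistic, not that the plan commits itself to a wrong inference.

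Third, the figures rest on student measurements, which the plan itself qualifies: "While the students, who collected the preliminary data, were not expert ultrasonographers". The trial uses one experienced examiner and ink marks, and it recruits people expected to have asymmetry. The left-right correlation and the size of the error may both differ. This also stands: the table above does not bound what the trial will find.

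Fourth, limits of agreement describe individuals, whereas the planned t tests and regressions compare group means. That is true, and it is why the added figures inform the measurement conclusion and not the test of OMT.

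**Conclusion.** The gap is real and moderate. No reliability statistic is planned for the left-right difference, and the ICC sentence is not tied to the control group that three other sections name for stability. Under the Table 1 SDs, equal ICCs on both sides and independent errors, a one-side SSD ICC of 0.80 corresponds to about 0.54 for the difference. Other plausible assumptions move this between about 0.34 and 0.77. If the errors were as strongly correlated as the measurements (0.565), the loss would vanish. The reliability of the difference therefore has to be estimated and cannot be read from the one-side ICC.

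Two stronger readings are not supported.

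- A reader might infer that the OMT comparison is biased. It is not: the same measurement error is present in both randomised arms.
- A reader might set the control total change expected from error alone (0.53, 0.44 or 0.31 cm at R = 0.70, 0.80, 0.90 with c = 0) against the 0.5 cm planning difference, and conclude that the effect is lost in noise. These are unlike quantities. The first is a noise level common to both arms; the second is a difference between arm means.

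**What to change.** In the Data analysis section:

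- State that the reliability ICCs use the control group, as sections A and C and Potential Limitations already intend, and name the form of ICC.
- Add, in controls, for the signed left-right difference in SSB, SPSIS and SSD: the mean first-to-second change, the within-person SD (or 95% limits of agreement) in cm, and an ICC with 95% CI.
- Have any conclusion about reliability for OMT outcomes cite these figures. Keep the one-side ICCs and their labels for landmark localization.

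The cost is one clarifying phrase and a short summary for each of three landmarks, from data already collected. The downside is precision. With 20 controls, an ICC of 0.77 has a 95% CI of 0.51 to 0.90, against 0.61 to 0.87 with 40 participants (one-way F interval). A within-person SD has a CI of 0.76 to 1.46 times its estimate, against 0.82 to 1.28 (chi-square, 19 and 39 df). The reported reliability may also look less favourable.

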### Potential Limitations

The primary limitation to the ultrasound measurements is maintaining consistency in location of the initial and second ultrasound measurements. This limitation will be addressed by using a single, highly experienced ultrasound examiner. To ensure that the ultrasound measurements are made at the exact same locations during the initial and second ultrasound assessments on an individual participant, the

ultrasound examiner will mark the skin overlying the measurement locations using waterproof ink. The use of multiple types of OMT techniques in this study may introduce some potential treatment bias; however multiple techniques are typically used in on a single patient in a clinical setting. Future studies could assess the efficacy of individual techniques to improve asymmetry. The control group will be used to evaluate whether the ultrasound sacral measurements are stable over a period of time. To determine if participant sex, age, or BMI affect the reliability of the ultrasound or palpitory assessments, additional analyses may be run to assess if participant sex, age, or BMI confound the percent agreement between the two assessments.

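### Aim 1 asks whether ultrasound depths are stable in untreated participants, but no named analysis estimates the mean signed first-to-second change in the control group

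*Combined protocol and SAP*

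**What the plan says.** The first aim in Specific Aims reads: "Determine if ultrasound measurements of sacral landmarks are stable over 30 minutes in untreated participants". Potential Limitations says who provides the evidence: "The control group will be used to evaluate whether the ultrasound sacral measurements are stable over a period of time".

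The Data analysis section offers two kinds of first-to-second statistic.

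- **Asymmetry quantities.** Absolute asymmetry, direction of change and total change are all built from left minus right. Total change is introduced with the words "To account for total change in measurements at both left and right landmarks between the first and second US measurements". Every test attached to these is between groups: a Fisher exact test of direction against group, regression models with group, and "mean total change in asymmetry for seated control and OMT groups will be compared using a 2-sample t test".
- **Reliability.** To judge whether ultrasound localisation is reliable, "intraclass correlation coefficients (ICC) and associated 95% CIs will be calculated for US measurements from the first to second US assessment for each landmark". The grading is: "For ICC, 0.7 to 0.8 was considered good; 0.8 to 0.9, very good; and 0.9 to 1.0, excellent".

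Two more general statements bear on the point. The Ultrasound Assessment section says that measurements before and after the intervention period will be compared, and Data analysis plans means, ranges and SDs for continuous variables. Neither is tied to the control group, to a method for paired change, or to a conclusion about stability.

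**The concern.** Stability in untreated people is a statement about how far the second reading lies from the first in the same person, on average and individually. The plan names no mean paired change in controls, no confidence interval for it and no limits of agreement.

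A systematic shift is conceivable from the design. Palpation comes before the first scan only. Controls leave, wait in another room, and lie prone again for the second scan. Contact pressure is to be kept consistent, but no measurement of it is described. Any of these could move left and right readings together, which is the pattern the asymmetry formulas cannot show. The ICC would then be the main formal evidence, and it mostly reflects how much people differ from one another. At stake is a report that readings are stable when they have moved by a few millimetres.

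**Working it through.** **Plan's own figure.** There is none to reproduce here: no ICC target and no tolerable shift is stated. The sample-size figure (38 participants, 0.5 cm) concerns SSDD, a right-left difference, and is not used below.

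**Inputs.** Left-side SDs from Table 1: SSB 0.96, SPSIS 0.81, SSD 0.59 cm. Controls: 20. Assumed, because the documents do not give it: within-person error SD e from 0 to 0.20 cm. The systematic shift d is hypothetical.

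**Step 1: asymmetry formulas.** Let L and R be the left and right readings.

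- Equal shift, L2 = L1 + d and R2 = R1 + d: L2 − R2 = L1 − R1. Absolute asymmetry and direction are unchanged, and total change is 0.
- Left side only, d = 0.3: total change = |(L1 − R1) − (L1 + 0.3 − R1)| = 0.3.
- Left 0.3, right 0.1: total change = 0.2.

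Only the equal shift vanishes.

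**Step 2: ICC.** With total variance s² and error variance e²:

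- consistency ICC = (s² − e²)/s², which does not contain d;
- absolute-agreement ICC = (s² − e²)/(s² + d²/2).

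Example, SSB with d = 0.3 and e = 0.20: (0.9216 − 0.04)/(0.9216 + 0.045) = 0.8816/0.9666 = 0.912.

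Each range below runs from e = 0 to e = 0.20.

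| Landmark | s² | Consistency, any d | Agreement, d = 0.2 | Agreement, d = 0.3 | Agreement, d = 0.5 |
|---|---|---|---|---|---|
| SSB | 0.9216 | 1.000 to 0.957 | 0.979 to 0.936 | 0.953 to 0.912 | 0.881 to 0.842 |
| SPSIS | 0.6561 | 1.000 to 0.939 | 0.970 to 0.911 | 0.936 to 0.879 | 0.840 to 0.789 |
| SSD | 0.3481 | 1.000 to 0.885 | 0.946 to 0.837 | 0.886 to 0.784 | 0.736 to 0.651 |

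At 0.2 cm, SSB and SPSIS are graded excellent throughout. At 0.3 cm, all values are excellent or very good except SSD near the top of the error range, which is good.

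The ICC also cannot separate shift from noise. For SSB, d = 0.3 with e = 0 gives 0.953, while d = 0 with e = 0.20 gives (0.9216 − 0.04)/0.9216 = 0.957. The two situations are practically indistinguishable by ICC, yet only one contains a systematic shift.

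SSD is a difference of two depths. If e = 0.20 applied independently to each, its error variance would be 0.04 + 0.04 = 0.08, and agreement would be 0.2681/0.3481 = 0.770 with no shift and 0.2681/0.3931 = 0.682 with d = 0.3.

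**Step 3: what a paired analysis of the 20 controls would show, on the same error SDs.** At e = 0.20 the SD of change is 0.20 × √2 = 0.283 cm and the standard error is 0.283/√20 = 0.063 cm. The 95% CI half-width is 2.093 × 0.063 = 0.13 cm. In simulation (1,000 runs per setting), a paired t test detected a 0.2 cm shift in about 100%, 98% and 84 to 85% of runs at e = 0.10, 0.15 and 0.20. It detected a 0.3 cm shift in about 99% or more throughout.

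Direct contrast at d = 0.2 and e = 0.15: the absolute-agreement ICC was at least 0.90 in 97% of runs for SSB and 88% for SPSIS, while the paired test rejected in about 98% for each.

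**The case against.** The strongest reply has four parts.

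- **The plan limits drift by design.** Sites are marked in ink, one experienced and blinded examiner does the scans, and contact pressure is kept consistent. This stands as mitigation, and the documents contain no evidence that a drift of 0.2 to 0.3 cm occurs. But Aim 1 sets out to test stability, so it cannot be assumed.
- **A shift could be seen anyway.** Means by visit and group, or the general before-and-after comparison, could show it informally. True. Neither has a stated method or group, so neither replaces a named estimate with its interval.
- **The ICC does react.** Under absolute agreement it falls with the shift, and SSD leaves the excellent band by about 0.3 cm even with no random error. A reader might infer that the ICC stays excellent whatever happens. That holds without regard to shift only for a consistency ICC with small error, and the plan does not say which form it will use.
- **Cancelling is a merit for Aim 2.** A reader might infer that a hidden drift undermines the treatment comparison, or could approach the 0.5 cm used for sizing. The documents support neither. Aim 2 concerns relative asymmetry between randomised groups, and an equal bilateral shift contributes zero to it. The 0.5 cm refers to SSDD, to which the same shift also contributes zero.

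Finally, the plan states no rule that an excellent ICC means stable. That is so, but it names no other formal statistic directed at the size of change in controls.

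**Conclusion.** The point holds for Aim 1 only. No named analysis estimates the mean signed first-to-second change in untreated participants. An equal bilateral shift is invisible to every asymmetry quantity. An ICC of unstated form and group is a weak guard: a 0.2 cm shift would still be graded excellent for SSB and SPSIS, and at 0.3 cm nearly all values would be very good or excellent.

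These sizes rest on the assumed error SD of 0 to 0.20 cm and on Table 1 SDs, which come from student operators. A smaller between-person SD in the trial, or a larger error in SSD, would lower the ICCs. It should not be read as saying that all shifts cancel, since unequal and one-sided ones do not, or that drift is present. If the ICC were computed in all 40 participants, it would also mix treated people into a question about untreated ones.

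**What to change.** Add to Data analysis, for Aim 1 and in the control group only: for SPSIS, SSB and SSD on each side, and for the signed left-right difference of each, report the mean signed change (second minus first) with its 95% CI and the limits of agreement. Base the stability statement on these. Keep the ICC as supporting evidence, specified as absolute agreement and computed in controls for Aim 1. Saying in advance how large a change would count as unstable would sharpen the conclusion, though the point does not depend on it.

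The cost is a short paragraph and a little more analysis of data already being collected. The downside is that a claim of stability becomes harder to meet.
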